### **4.4. Study Days and Visits**

For by-visit summaries, if there are multiple assessments at a post baseline visit then the last non-missing assessment at that visit will be used for the summary (this includes scheduled and unscheduled assessments).

Study days are numbered relative to the first day of study drug administration. The start of treatment (Day 1, Visit 4) is defined as the date on which a patient takes the first dose of study drug, as recorded on the study drug diary. Days will be numbered relative to treatment start (i.e., ..., -2, -1, 1, 2, ...; with day 1 being the first day of study drug administration and day -1 being the day before the first day of study drug administration). For details of study days and visits, see Table 1.

## **5. STUDY POPULATION**

### **5.1. General**

With the exception of brief physical examination reported in Part 2 only (see Table 1), where only ITT analysis set will be used and ACQ-6 questionnaire used for entry criteria at Screening for patients with asthma only, all analyses detailed in section 5 will be based on the enrolled analysis set (Part 1) and on the ITT analysis set (Part 2) as well, unless otherwise specified.

For analysis performed on the enrolled analysis set, summaries will be presented by study participants status (Healthy Control Subjects (HCs), n=5)) vs. patients with asthma, n=10) and overall (n=15).

For analysis performed on the ITT analysis set, FAS or safety set summaries will be presented by treatment group (reslizumab (n=5) vs. placebo, n=5)) and overall (n=10).

### **5.2. Patient Disposition**

For Part 1, data from patients screened, subjects/patients enrolled, not enrolled (i.e., screen failure and reason for failure), subjects/patients completed Part 1, subjects/patients who withdraw from Part 1 with reason for withdrawal. For Part 2, patients enrolled but not randomized (and reason for not randomized), patients who are randomized (ITT analysis set), patients randomized but not treated, safety, and full analysis sets, patients who complete the study and patients who withdraw from the study with reason for withdrawal, will be summarized using descriptive statistics (Summary 15.1.1.1).

### **5.3. Demographics and Baseline Characteristics**

Patients and HC subjects demographics: age (years), sex (male, female), height (cm), weight (kg), body mass index (BMI, kg/m^2), ethnicity (Not Hispanic or Latino, Hispanic or Latino, unknown), race (white, black or African American, Asian, American Indian or Alaskan Native, Native Hawaiian or other Pacific Islander, other), and baseline characteristics including tobacco usage: smoker or not, current or former user (never used, formerly used, currently uses), number of non-smoking years, number of smoking years, number of packs per days, will be summarized for Part 1 based on the enrolled analysis set (Summaries 15.1.2.1 and 15.1.2.3) and for Part 2 based on the ITT analysis set (Summaries 15.1.2.2 and 15.1.2.4), using descriptive summary statistics.

Airway reversibility testing using spirometry will be summarized for Part 1 using the enrolled analysis set and for Part 2 using the ITT analysis set (Summaries 15.1.3.1 and 15.1.3.2, respectively).

Similarly, clinical laboratory tests (see Table 4 of the protocol) performed at screening visit will be summarized for serum laboratory chemistry tests, serum laboratory hematology tests, and urinalysis laboratory tests based on the enrolled analysis set (Summaries 15.1.4.1, 15.1.4.2, and 15.1.4.3, respectively).

Serum  $\beta$ -HCG test performed at screening will be summarized (n, %) by beta-HCG category (negative, borderline, and positive) and participants group (HCs, asthma patients) based on enrolled analysis (Summary 15.1.4.4). Positive/borderline values will be listed by individual participants for the enrolled analysis set.

Vital signs at screening visit, including pulse rate, systolic/diastolic blood pressure, respiratory rate, temperature and oxygen saturation, will be summarized, by participants group (HCs, asthma patients), for enrolled analysis set (Summary 15.1.5.1).

Moreover, number and percentages of patients/subjects (Part 1) with at least one abnormal physical examination finding at screening visit will be summarized, by participants group and overall, based on the enrolled analysis set (Summary 15.1.6.1). Similarly, for Part 2, number and percentages of patients with at least one abnormal physical examination finding at each visit will be summarized by visit (4, 5, 6, and 7) and treatment group (reslizumab, placebo and overall) based on the safety analysis set (Summary 15.3.4.1).

Any physical examination finding that is judged by the investigator as clinically significant will be considered as an adverse event and listed as such.

#### **5.4. Medical History**

All medical history will be coded using the latest available version of Medical Dictionary for Regulatory Activities (MedDRA).

The incidence of general medical history abnormalities will be summarized using descriptive statistics (n, %) by system organ class (SOC) and preferred term. Patients/subjects are counted only once in each preferred term and SOC category. Summaries will be presented by study participants group (Asthma patients versus HC subjects) and overall (Summary 15.1.7.1) based on the enrolled analysis set, and by treatment group (Reslizumab versus Placebo) and overall (Summary 15.1.7.2) based on safety analysis set.

Asthma/allergic history are recorded on the CRF. The incidence of following asthma/allergic histories (asthma, chronic sinusitis, atopic dermatitis, aspirin rhinitis, ever received allergy shots, presence of pets at home, food allergy, eosinophilic esophagitis, asthma exacerbations requiring systemic corticosteroids within the last 12 months, patient was hospitalized or visited the emergency department for asthma within the last 12 month, history of intubation for asthma exacerbation, history of ICU admission for asthma exacerbation, days missed from school/work due to asthma in the last 12 months) will be summarized, by study participants group, based on the enrolled analysis set (Summary 15.1.7.3) and by treatment group, based on the safety analysis set (Summary 15.1.7.4), using descriptive statistics. Patients are counted only once in asthma/allergic histories.

The anteriority of the first diagnosis and of the most recent event and the number of events will be summarized by asthma/ allergies history abnormalities.

The ACQ-6 is a validated asthma assessment tool performed at Screening (Visit 1) as entry criterion six questions self-assessments questionnaire completed by the patients only. The Healthy subjects do not use this tool. Each question on the ACQ-6 is scored on 7-point scale ranging from 0 to 6, and the total score is the mean of all responses (see Appendix A of the protocol and Juniper et al (1999)). The total score will be summarized, by treatment group, based on the ITT analysis set using descriptive statistics (Summary 15.1.7.5).

Nasal polyps history are recorded on the CRF. The incidence of nasal polyps history abnormalities will be summarized using descriptive statistics (n, %). Patients/subjects are counted only once. Sinus surgery performed (Y/N), anteriority of the surgery (years), diagnosed by CT scan (Y/N), anteriority of the CT scan (years) and anosmia will be summarized, by study participants group based on the enrolled analysis set for Part I (Summary 15.1.7.6), and by treatment group based on the safety analysis set for Part II (Summary 15.1.7.7), using descriptive statistics.

### **5.5. Prior therapy and Medication**

Any prior medication, treatment, or procedure a patient/subject has had within 4 weeks before screening and stopped before the first study visit (screening) will be recorded on the CRF.

Generic or trade name, indication, and dosage will be recorded. The sponsor will encode all therapy and medication according to the latest version of the World Health Organization drug dictionary (WHO Drug)

The incidence of prior therapies and medications will be summarized using descriptive statistics (n, %) by therapeutic class and preferred term and study participants, based on the enrolled analysis set for Part I (Summary 15.1.8.1), and by therapeutic class/preferred term and treatment group based on the safety analysis set for Part II (Summary 15.1.8.2). Patients/subjects are counted only once in each therapeutic class category, and only once in each preferred term category. Prior therapies and medications will include all medications taken and therapies administered before the first day of study drug administration.

For details of allowed prior medications (with restrictions) and not allowed medications during the study, see section 5.3 of the protocol.

### **5.6. Electrocardiography**

A 12-lead ECG values collected at Screening (ECG mean hear rate, PR interval, QRS duration, QT interval, QTcB interval, QTcF interval, and RR interval) and the proportion of normal ECG, non-clinically significant abnormality and clinically significant abnormality at screening will be summarized, by study participants group and overall based on the enrolled analysis set (Summary 15.1.9.1) and safety analysis set (Summary 15.1.9.2), using descriptive statistics (n, %).

### **5.7. Childbearing Potential and Methods of Contraception**

For female patients, information related to childbearing potential, and menopause will be collected. Childbearing potential (Y/N), birth control method [combined (estrogen and gestagen) oral contraceptives, hormone implants, hormone rings, contraceptive patch, hormones injectables, progesterone only hormonal contraception, other] , barrier methods of contraception (diaphragm with spermicide, portio cap with spermicide, condoms with spermicide, other), intrauterine device (copper, hormonal, none), abstinence (Y/N), surgically sterilized (Y/N), menopause age, documented hysterectomy (Y/N), bilateral oophorectomy or salpingectomy (Y/N) will be summarized, using descriptive summary statistics, by study participants group and overall based

on the enrolled analysis set (Summary 15.1.10.1), and by treatment group and overall based on the safety analysis set (Summary 15.1.10.2).

A serum  $\beta$ -HCG pregnancy test will be performed at V1 (Screening) only, for all participating women of childbearing potential. Data will be summarized (n, %) by beta-HCG category (negative, borderline, and positive) and participants group (HCs, asthma patients) based on enrolled analysis (Summary 15.1.4.4), and will be listed.

Urine  $\beta$ -HCG tests will be performed, for all participating women of childbearing potential, at V2, V3, V5, V6, and V7, prior to performance of PET/CT scan and will be listed.

## **5.8. Study Protocol Violations**

Subjects/patients with any protocol violations (as recorded in protocol violation CRF) during the study will be summarized by violation classification category and overall using descriptive statistics (n, %) for the enrolled analysis set (Part 1: Summary 15.1.11.1) and for the ITT analysis set (Part 2: Summary 15.1.11.2). Subjects/patients will be counted only once in each violation category for the summary purpose. Data will be listed.

All instances of medication errors, overdose, misuse, abuse, off-label use, and occupational exposure will be summarized in category “Non-Compliance to study investigational medical product (IMP).”

For definition of protocol violations, see sections 11.1.2 and 7.3 of the protocol.

## 6. EFFICACY ANALYSIS

### 6.1. General

The study is composed of two parts with two primary objectives.

The enrolled analysis set will be used for the part 1 analysis (summaries and listings). Summaries will be presented by participants status [HC subjects (n=5) vs. patients with asthma (n=10)] and overall.

The ITT analysis set will be used for the summaries and presentations of the primary and secondary efficacy endpoints and the FAS analysis set will be used for all efficacy and exploratory analyses for the Part 2 data. Summaries will be presented by treatment group (reslizumab vs. placebo) and overall.

### 6.2. Primary Efficacy Endpoint and Analysis

#### 6.2.1. Definition

The primary efficacy measure for this study is the change in GLG as assessed by PET/CT.

Part 1 of the study will validate this measure by comparing this assessment between HC subjects and patients with eosinophilia asthma.

In Part 1, the primary efficacy endpoint is the intra-patient variability (reproducibility measurement) in each group and inter-group variability between HC group and individual patients with eosinophilic asthma.

In Part 2, only patients with eosinophilic asthma will be assessed for GLG at 2, 4, and 6 weeks, after randomization to placebo or treatment with a single dose of reslizumab.

In Part 2, the primary efficacy endpoint is the change from baseline to week 4 in GLG ( $\Delta$ GLG).

The radiology center at [REDACTED] will determine the following:

GLG is the total FDG uptake in the whole lung.

A region of interest (ROI) is drawn around lung boundary in each axial slice. SUVmean and area of each ROI is recorded. Using the formula:  $area * slice\ thickness$ , the volume of each slice is calculated. Then SUVmean of each slice is multiplied by the volume of the corresponding slice, which will represent the total FDG uptake in one slice. This product for each slice is summed over number of slices to provide GLG of that lung for each subject/patient as follows:

$$GLG = \sum_1^n (area * slice\ thickness * SUV\ mean)$$

n=number of slices

Intra-subject/patient variability (reproducibility measurement (Part 1)) :

Below is the calculation to determine the intra-individual variability between PET/CT scans as measured by GLG for HC subjects and patients with eosinophilic asthma. The accepted variability within each group is  $\leq 10\%$  and will be calculated as follows:

Relative difference of **GLG (HCs)** =  $(GLG2-GLG1)/GLG1$  (For HC subjects)

Relative difference of **GLG (patients with eosinophilic asthma)** =  $(GLG4-GLG3)/GLG3$  (For patients)

1= First measurement (HCs)

2= Second measurement (HCs)

3= First measurement (patients with eosinophilic asthma)

4= Second measurement (patients with eosinophilic asthma)

A 10% variability (measured as a relative difference between the first measurement and second measurement) between PET/CT scans as measured by GLG within each group (HCs, n=5) and patients (n=10), will be considered as the maximum allowed intra-group variability.

Relative differences between the first (V2) and second (V3) measurements will be summarized, by total/regional lung and patients/HC group, using descriptive summary statistics, based on enrolled analysis set (Summary 15.2.1.1).

Variability between HC group and individual patients with eosinophilic asthma (Part 1):

The planned method to assess whether the difference in GLG measure between HC subjects, as a group, and individual patients (one-by-one) with eosinophilic asthma is  $\geq 5\%$  will be calculated as follows:

- For Females: Relative difference of GLG =  $(GLG6i-GLG5f)/GLG5f$ , i.e., difference in GLG (based on average of 2 measurements) between each individual patient with asthma and the mean of HC group, for females.
- For Males: Relative difference of GLG =  $(GLG6i-GLG5m)/GLG5m$ , i.e., difference in GLG (based on average of 2 measurements) between each individual patient with asthma and the mean of HC group, for males.

5=average of 2 GLG measurements (1 and 2) of all HCs by sex

6=average 2 GLG measurements (3 and 4) for each individual asthma patients

GLG6i will be calculated for each individual male/female patient using his/her two GLG measurements at V2 and V3 (Part 1). If this amount is  $\geq 5\%$  then the patient will be randomized.

Relative differences in GLG measures between the HC group and individual patients with asthma will be summarized for each sex, by total lung/regional lung, using descriptive summary statistics, based on enrolled analysis set (Summaries 15.2.1.2 and 15.2.1.3).

Relative change from baseline to week X in GLG ( $\Delta$ GLG) (Part 2):

$\Delta$ GLG =  $(GLGwX - GLG_{baseline})/GLG_{baseline}$

wX= post-randomization week (week 2 /V5, week 4/V6, and week 6/V7).

GLG Baseline= the average of two measurements at Visits 2 and 3 of Part 1 (see section 4.2 of the SAP).

#### SUV mean:

SUV is a well validated measure which normalizes FDG uptake by any particular object/tissue volume by the administered dose and either total body weight or total body surface area. Regions of interest (ROIs) will be drawn manually around the outer boundaries of the lung on every transverse slice passing through the lung on fused FDG PET/CT images from each subject. The trachea and main stem bronchi will be excluded from the ROIs to capture only the inflammation in the lung parenchyma. Lung sectional mean standardized uptake value (sSUV mean) and the area of the lung ROI will be recorded from each slice. Subsequently, the sectional lung volume (sLV) will be calculated from each slice by multiplying the lung ROI area (in centimeters squared) by 0.4 (slice thickness 4 mm). The sectional lung glycolysis (sLG) will be determined by multiplying sLV and lung sSUV mean from each slice. The lung volume (LV) will be calculated by adding all the sLV from slices passing through the lung, and the global lung glycolysis (GLG) will be determined by adding all the sLG from slices passing through the lung.

Finally, the lung SUV mean will be calculated as follows:

$$\text{SUV} = \text{GLG}/\text{LV}.$$

Similar methodology is applied to lymph nodes and bone marrow. See section 6.4.3 of this SAP.

#### **6.2.2. Primary Efficacy Analysis**

For Part 1, intra-group variability and variability between HC group and individual patients with eosinophilic asthma data and all variables which enter into these calculations will be listed.

For Part 2, change in GLG from baseline to each of the postbaseline visits (2, 4, and 6 weeks, after randomization) will be summarized, using descriptive statistics (n, mean, standard deviation, median, minimum, and maximum), by treatment group (reslizumab vs placebo) for total and regional lung based on ITT and FAS. The difference in mean changes from baseline between reslizumab and placebo will also be summarized and reported (Summaries 15.2.2.1 to 15.2.2.8).

No inferential statistics will be used for the primary endpoints analyses.

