6.1.3. Calculations

The radiology center will determine the following:

GLG is the total FDG uptake in the whole lung.

An ROI is drawn around lung boundary in each axial slice. SUVmean and area of each ROI is recorded. Using the formula: area*slice thickness the volume of each slice is calculated. Then SUVmean of each slice is multiplied by the volume of the corresponding slice, which will represent the total FDG uptake in one slice. This number for each slice is summed together to provide GLG of that lung.

$$GLG = \sum_1^n (area * slice\ thickness * SUVmean)$$

n=number of slices

Intra-patient variability (reproducibility measure):

Below is the calculation to determine the intra-patient variability between PET/CT scans as measured by GLG for HCs and patients with eosinophilic asthma. The accepted variability within each group is $\leq 10\%$ and will be as follows:

Relative difference of GLG=(GLG2-GLG1)/GLG1

Relative difference of GLG=(GLG4-GLG3)/GLG3

1= First time point (HCs)

2= Second time point (HCs)

3= First time point (patients with eosinophilic asthma)

4= Second time point (patients with eosinophilic asthma)

Variability between HC group and individual patients with eosinophilic asthma:

The planned method to assess whether the difference in GLG (Δ GLG) between HC subjects, as a group, and individual patients with eosinophilic asthma is $\geq 5\%$ and will be as follows:

For Females:

Relative difference of GLG=(GLG6_i-GLG5f)/GLG5f

For Males:

Relative difference of GLG=(GLG6_i-GLG5m)/GLG5m

5=average of 1 and 2

6=average of 3 and 4

GLG6_i will be calculated for each individual patient using his/her two measurements, and if that amount is $\geq 5\%$, than the patient will be randomized.

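### Part 2 ΔGLG is never set against repeat-scan error, although for patients near the 5% entry window a full return to the control mean (-4.8%) could lie within that error

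*SAP*

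**What the plan says.** Entry to Part 2 rests on two GLG criteria (Protocol 4.1, criteria k and l; Protocol 6.1.3; SAP 6.2.1).

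- **Signal window.** The patient's excess over controls must be at least 5%. For women the SAP defines it as "difference in GLG (based on average of 2 measurements) between each individual patient with asthma and the mean of HC group, for females", with a matching formula for men.
- **Reproducibility.** The two untreated scans may differ by no more than 10% in relative terms, a figure that the SAP says "will be considered as the maximum allowed intra-group variability".

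The Part 2 endpoint is the relative change from baseline, where "GLG Baseline= the average of two measurements at Visits 2 and 3 of Part 1". Each post-dose value is one scan. SAP 6.2.2 then states that "change in GLG from baseline to each of the postbaseline visits (2, 4, and 6 weeks, after randomization) will be summarized" as n, mean, SD, median, minimum and maximum by arm, together with the difference in mean changes. The same section excludes inferential statistics.

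The visit 2/visit 3 differences appear in three places: as an entry criterion, as a Part 1 summary (15.2.1.1) and in a Part 1 listing. The Part 2 analysis sections contain no within-subject SD, repeatability limit or interval for ΔGLG.

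**The concern.** The second primary objective (SAP 1.1.1) is to show that reslizumab lowers the lung signal. SAP 6.3 then correlates ΔGLG with the secondary endpoints as a measure of imaging benefit. Both uses need some idea of how large a change the scan produces without treatment.

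The entry rules allow a patient to have little excess signal to lose while tolerating repeat differences about twice that size. A fall of 5% to 8% in such a patient could be drug effect or scan noise, and the planned tables would not help a reader to tell which. The repeat-scan design already collects the data needed.

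**Working it through.** The documents give no SD, effect size or power for GLG (SAP 2.4), so there is no planned figure to reproduce. The inputs are the 5% window, the 10% cap, the two-scan baseline, single post-dose scans and 5 patients per arm. The cap is read as applying to the absolute difference.

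**1. Loss on return to the control mean.** With baseline = (1 + w) × control mean, ΔGLG = 1/(1 + w) - 1.

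| Excess at entry, w | ΔGLG on return to control mean |
|---|---|
| 5% | -4.8% (5/105) |
| 10% | -9.1% |
| 15% | -13.0% |
| 20% | -16.7% |

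**2. An example that needs no distribution.** Let the control mean be 1.00, visit 2 = 1.00 and visit 3 = 1.10. The repeat difference is 10% and the baseline 1.05 is 5% above controls, so the patient enters. An untreated week-4 scan of 1.00 gives 1.00/1.05 - 1 = -4.8%, the same as complete normalisation at the window.

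**3. Scan error in ΔGLG.** Let sw be the within-subject SD of one scan, in percent. A repeat difference has SD sw·√2. ΔGLG sets one scan against a mean of two, so its SD is sw·√(1 + 1/2) = sw·√1.5.

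Assume that 10% is the 95% limit of repeat differences:
- sw = 10/(1.96·√2) = 3.61
- SD(ΔGLG) = 3.61·√1.5 = 4.42
- 95% limit for one untreated patient = 1.96 × 4.42 = ±8.7%
- chance of an untreated fall of 4.76% or more = Φ(-4.76/4.42) = 14%

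**4. Arm difference, scan error only.** SE = 4.42·√(2/5) = 2.79. The 95% half-width is 1.96 × 2.79 = 5.5 points if the SD is taken as known, or 2.306 × 2.79 = 6.4 points with t on 8 df.

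**5. Sensitivity to the reading of the cap.**

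| Assumption | sw | One-patient 95% limit |
|---|---|---|
| 5% is the 95% limit (repeatability twice as good) | 1.80 | ±4.3% |
| 10% is the 95% limit | 3.61 | ±8.7% |
| 10% covers only 80% of repeats | 5.52 | ±13.2% |

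The one-patient limit equals 4.76% when the SD of the repeat difference is 4.76/(1.96 × √0.75) = 2.8%. Below that value, normalisation at the window would stand clear of scan error.

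**6. Excess at which the problem goes away.** Against ±8.66%, return to the control mean exceeds the limit once w is above 1/(1 - 0.0866) - 1 = 9.5%.

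**The case against.** The 5% is a minimum and the 10% a maximum, and neither is an expected value. A reader might infer that 4.8% is the most a treated patient can lose, and so that Part 2 cannot show an effect. The documents do not support that. They do not say that the control mean is a floor or that the drug effect equals the excess over it. That mean comes from only 2 or 3 controls of each sex (Protocol 1.7), and a patient who starts 20% above it could fall 16.7% by returning to it. Setting the arm-level half-width against 4.8% would also require every treated patient to sit at the threshold. This objection stands.

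The cap is not an estimated error, and on the better-repeatability reading the conclusion reverses. This also stands, and it is a reason to estimate the error.

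The randomised placebo arm has ΔGLG of the same structure over the same weeks. It also carries the same regression to the mean, which arises because the visit 2 and 3 scans both select patients as high and serve as their baseline. With the Part 1 listings, a reader could derive a repeatability figure. This stands in part: noise is visible indirectly, but with five per arm and no interval the difference in means has nothing beside it to judge it by.

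Descriptive analysis is a declared choice in an exploratory study, and the plan defines no responder. Both are true. The absence of a repeatability limit is a missed aid to interpretation, not a contradiction.

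**Conclusion.** The point holds in a limited form. For patients near the window, full return to the control mean (-4.8%) could lie within scan-repeat error: about ±8.7% for one patient if 10% is the 95% limit of repeat differences, and about ±4% to ±13% over the readings tried. It need not do so if the SD of repeat differences is below about 2.8%, or for patients who start well above the window. SAP 6.2.2 never makes the comparison, and it reports the arm difference without a measure of uncertainty.

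A reader might also conclude that a change inside the limits should not count as a reduction. That goes too far. With limits of ±8.7%, a 6% fall in all five treated patients would score zero, although the consistency is itself evidence. The limits should serve as a reference, not a rule.

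This is an inexpensive improvement to how objective 2 is read. It does not show that the design is invalid or that more patients are needed.

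**What to change.** In SAP 6.2.2:

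1. For every visit 2/visit 3 pair in the enrolled set, compute d = the difference in ln GLG. Include patients who fail criterion k, so that the estimate is not truncated by the entry rule. Estimate sw = sqrt(mean(d²)/2), and report it for controls, for patients and pooled, because pooling assumes equal error.
2. List or plot each patient's ΔGLG at weeks 2, 4 and 6 by arm beside the reference limits ±1.96·sw·√1.5, labelled as descriptive. The limits are on the log scale and can be back-transformed: ±0.0866 becomes exp(-0.0866) - 1 = -8.3% and exp(0.0866) - 1 = +9.0%.
3. Give the arm difference in mean ΔGLG with a 95% confidence interval, stated to be descriptive so that it agrees with the exclusion of inferential statistics.
4. State the limitations beside the table. About 15 pairs estimate sw imprecisely: the 95% range is roughly 0.74 to 1.55 times, so ±8.7% could be about ±6.4% to ±13.4%. Repeats about 7 days apart (Protocol 3.1) may understate variation over 4 to 6 weeks.

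The cost is one derived quantity, one display and one interval from data already planned. No new scans are needed, and entry and treatment do not change. The small downside is that imprecise limits may be over-read, which item 4 addresses.
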